# 1. Introduction

Cerebral palsy (CP) occurs in 2 to 3.5 of 1000 live births, with spastic CP, accounting for the majority of cases (1,2). This is a specific form of hypertonia that leads to an imbalance of muscle forces, which presents in the abnormal position of the limb. These abnormal positions can interfere with various motions of the upper limb, such as grasp-to-release function and the tasks involved in activities of daily living (ADLs) (3).

Tendon transfer is a popular surgical option to correct these deformities, whilst botulinum toxin type A (BTX-A) is a common non-surgical option and can be used to delay surgery and reduce spasticity. Repeat injections are considered where the clinical effects have diminished, and new goals have been established.

BTX-A has been reported as a safe and effective treatment with the ability to enhance performance in school activities, ADLs (4) and functional movement (5), particularly in children with mild movement impairments (6). There was an observation of increased muscle volume in the non-injected muscle and decreased volume in the injected muscle following BTX-A treatment in a population of children with spastic CP (7). Additionally, it has been found that BTX-A can induce muscle weakness in the target and non-target muscles (8,9), but there is little knowledge of how the mechanical properties of muscles contribute to this induced muscle weakness. Where a patient may require a tendon transfer surgery, following BTX-A treatment, the properties of the involved tendons may affect the outcome of surgery, due to the contribution of tendon mechanical properties to force generation of the muscle-tendon unit (10). This raises the questions of how BTX-A induced adaptations affect the functional ability of the upper extremity and how these adaptations may affect length of treatment. Addressing these questions will give us an indication of when decisions should be made to continue BTX-A treatment or to begin to consider surgery. Moreover, it is important to know if the continuous use of BTX-A affects the performance of the associated tendon in future surgical intervention. Currently, no objective evaluation is done to assess muscle and tendon mechanical properties prior to surgical intervention.

In order to build on the knowledge of the effects BTX-A has on the upper extremity, clinical hand assessments will be used in conjunction with biomechanical tools to investigate the mechanical and anthropometric adaptations. A novel technology, shear-wave elastography (SWE) will be used to evaluate the properties of muscles and tendons before and after BTX-A injections. The comparison of data collected before and after BTX-A treatment will inform the BTX-A induced adaptations. The data obtained from this study will be used to contribute to computational models in order to identify limits of suitability for a muscle or tendon to aid in surgical treatment.

This study will provide insight of the biomechanical adaptations of muscles and tendons after BTX-A treatment and how they contribute to joint function among a population of children with spastic CP. This will bring more understanding of the general behaviour of the musculoskeletal system following treatment which will benefit muscle and tendon selection for monitoring purposes or prospective surgical interventions and allow for a more objective guideline to be implemented.

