## 3.1 Inclusion Criteria

- 1. Participants must be aged between 4 and 18 years.
- 2. Participants must be diagnosed with spastic cerebral palsy in at least one of their upper limbs.
- 3. Participants must be due to start BTX-A treatment for their affected upper limb.
- 4. Participants must have minimum ability to hold an object and stabilise it for use by the other hand.
- 5. Participants must be able to comprehend and complete the test protocol.
- 6. Participant or the participants parent/carer must be able to speak, read and understand English, in order to be involved in this study.

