# 4. Study Design

## 4.1 Methodology

Participants will be asked to take part in all the tests listed below. This will take approximately 1 hour in total. The participants will attend three sessions at the 1st Floor, Paediatric Outpatients, Chelsea and Westminster Hospital ([name]). The first session being before they start BTX-A treatment, the second session will be between 3 weeks and 6 months after treatment and the third session will be at least 6 months after treatment. All the sessions will consist of the procedures described in sections 4.1.1, 4.1.2 and 4.1.3.

Upon arrival at the 1st Floor, Paediatric Outpatients Department, participants' carers will be asked to review the participant information sheet and sign the consent form, if they have not already done so. If the participant is over the age of 16 years of age, they will be asked to sign a consent form. For participants under the age of 16, they will sign an assent form. Demographic information regarding the participant's age (current year and month), diagnosis and any significant birth history or previous surgery will be documented. Participants must consent to the clinical care team

reviewing the ultrasound scan reports to ensure any incidental findings can be appropriately investigated and acted upon.

A camera with a tripod, will be used to video record future data processing. The participant will be seated at a table and the camera will be focused on the participant's upper extremity and the tabletop. For the best observation of participant's extremity, long hair will be restrained, if possible, and their sleeves will be rolled up above the elbow. The participant will be positioned sideways to the camera with uninvolved side closest to the camera and the involved side furthest from the camera. This position allows best visibility of the involved hand and thumb for the video.

Participants will be asked to take part in a series of three main activities: Shriners hospital upper extremity evaluation, ultrasound measurements and EMG measurements. Following each task, a 3-minute rest period will be designated in order to avoid the effects of fatigue.

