#### 4.1.2 Shear-wave elastography ultrasound measurements

#### (20 minutes)

Shear-wave elastography (SWE) is a novel ultrasound technology for characterising mechanical properties of soft tissues through dynamic measurement of tissue displacement as a result of mechanical excitation. A LOGIQ E10 Ultrasound R2 system (GE Healthcare, Chicago, IL, USA) with a ML6-15-D probe (GE Healthcare, Chicago, IL, USA) will be used to collect SWE measurements including the shear-wave velocity during the relaxed and stretched states of the origin and insertion tendons of the muscles to be injected with BTX-A. As the shear modulus is equal to the shear-wave velocity multiplied by the density of the tissue, this will provide information regarding the elasticity of the tissue. In addition to this, the ultrasound measurements can provide tissue anthropometrics such as tissue length and cross-

sectional area. This will provide insight of the biomechanical adaptations after BTX-A treatment and how they contribute to joint function.

For this task the investigator will apply ultrasound gel between the probe and the participant's skin at the region of interest to limit tissue deformation caused by the operator. As the shear-wave velocity is dependent on the probe orientation relative to the muscle fibres, all the SWE acquisitions will be performed parallel to the direction of the muscle fibres and perpendicular to the participant's skin. When the ultrasound probe is correctly aligned, the shear-wave velocity and a sequence of 10 continuous images will be recorded. This will be repeated for the each of the muscles involved in the participant's BTX-A treatment.

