## 4.4 Outcome measures

Primary outcome measure: The primary outcome measures are the elasticity of the tendons and the anthropometrics of the muscles before and after BTX-A injections.

Secondary outcome measure: The secondary outcome measure is the comparison of computational models for data collected before and after BTX-A injections.

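### With no body or limb size measure and no reference muscle listed, growth cannot be separated from a BTX-A effect on muscle length and cross-sectional area at session 3 or a late session 2

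*Protocol*

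**What the plan says.** The aim is causal: Protocol section 2.1 sets out to find what BTX-A does to the anthropometric and mechanical characteristics of muscle and tendon. The Introduction adds that "The comparison of data collected before and after BTX-A treatment will inform the BTX-A induced adaptations".

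Section 4.4 makes the primary outcome measures "the elasticity of the tendons and the anthropometrics of the muscles before and after BTX-A injections". Section 4.1.2 indicates what anthropometrics means: "the ultrasound measurements can provide tissue anthropometrics such as tissue length", together with cross-sectional area. The same section repeats the scan for each muscle in the child's BTX-A treatment and names no other muscle.

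On population and timing, section 3.1 states "Participants must be aged between 4 and 18 years" and admits only children about to start BTX-A. Section 4.1 puts the first session before treatment; then "the second session will be between 3 weeks and 6 months after treatment" and "the third session will be at least 6 months after treatment".

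On background data, section 4.1 says that "age (current year and month), diagnosis and any significant birth history or previous surgery will be documented". Height, weight and limb length are not in that list, and the equipment list in section 4.3 holds nothing to measure them with. Section 7 names a normality test followed by t-tests and ANOVA.

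**The concern.** Muscles lengthen and thicken as a child grows. In a before-after study of treated muscles, any change in length or area after several months is the sum of growth and treatment. To separate them, the study needs an untreated comparison (a group, a limb or a muscle) or a measure of how much the child or limb has grown. The protocol lists neither.

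Growth pushes length and CSA upwards. It can therefore appear as a gain that BTX-A did not cause, or offset a real loss of muscle size. Because the interval to session 3 is open-ended and growth rate depends on age, the bias differs between children and does not simply shift all results by one amount. Sections 1 and 2.2 intend the data for computational models of when a muscle or tendon is suitable for surgical use, so the error would carry forward into those models.

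**Working it through.** **Step 1. Can the listed data separate growth from treatment?**

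| Possible route | What the protocol provides |
|---|---|
| Untreated group | None described; all participants are due to start BTX-A (section 3.1) |
| Untreated limb or muscle | Scans repeated for treated muscles only (section 4.1.2) |
| Body or limb size at each session | Not listed (section 4.1); no tool for it (section 4.3) |
| Age | Listed |

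Age does not help. Within a child, age and time since injection advance by the same amount, so a change due to growth and a change due to treatment follow the same time axis. No route is open.

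**Step 2. How large could growth be?** The documents give no growth rate, so this is illustration only. Assumptions: height velocity v of 5.5 to 8 cm/year, height h of 105 to 150 cm, muscle size scaling with stature. For an interval of t years:

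- proportional length change g = v × t / h
- proportional CSA change = (1 + g)² − 1

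The low corner is v = 5.5, h = 150; the high corner is v = 8, h = 105.

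| Interval | Length, low | Length, high | CSA, low | CSA, high |
|---|---|---|---|---|
| 3 weeks (t = 3/52) | 0.2% | 0.4% | 0.4% | 0.9% |
| 6 months (t = 0.5) | 2.75/150 = 1.8% | 4/105 = 3.8% | 1.0183² − 1 = 3.7% | 1.0381² − 1 = 7.8% |
| 12 months (t = 1) | 5.5/150 = 3.7% | 8/105 = 7.6% | 1.0367² − 1 = 7.5% | 1.0762² − 1 = 15.8% |

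Twelve months is shown because section 4.1 permits it. For a participant who has stopped growing, v = 0 and every entry is zero.

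**Step 3. What could that do to a test?** Section 3.4 gives a sample size of 8. Assume a paired t-test with n = 8, two-sided alpha 0.05, and a standard deviation s of within-child percentage change of 5, 10 or 15%; the protocol gives none. The rejection probability comes from the noncentral t distribution with 7 degrees of freedom and noncentrality (mean change / s) × √8.

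No true BTX-A effect, growth only:

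| Mean CSA growth | s = 5% | s = 10% | s = 15% |
|---|---|---|---|
| 3.7% (6 months, low) | 0.44 | 0.15 | 0.09 |
| 7.8% (6 months, high) | 0.96 | 0.48 | 0.25 |

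The nominal value is 0.05 throughout.

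Masking, with an assumed true CSA loss of 10% and s = 10%: the mean change seen is −10% plus growth. Power is 0.68 with no growth, 0.40 with 3% CSA growth, 0.23 with 5% and 0.11 with 7%.

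The spread of these results shows that the effect on conclusions cannot be pinned down from the documents. That growth and treatment are inseparable does not depend on any of these figures.

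**The case against.** A reader might infer that the protocol commits to comparing raw, unscaled measurements. It does not say so. Image processing is left to custom software (section 4.2), the analysis is summarised in a few words (section 7), and a SAP not shown here could specify scaling or covariates. That stands, and for that reason the point is confined to what is listed for collection: a SAP cannot scale to a limb length that nobody measured.

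A reader might also infer that every before-after difference will be credited to BTX-A. The Introduction says only that the comparison will inform the adaptations. The causal aim in section 2.1 is the firmer ground, and it supports the narrower point that the design cannot isolate such an effect.

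The problem is not uniform across visits or children. A session 2 near 3 weeks is barely touched, and near-grown adolescents hardly at all. Tendon elasticity, the other part of the primary outcome, is not covered by this argument.

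On masking, the Introduction does cite reduced volume in injected muscle, but the title of that reference places it immediately after treatment, when growth bias is smallest. The documents do not predict a loss still present at 6 months, so masking is a possibility rather than an expected result.

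The eight healthy participants in section 3.4 might be taken for a control group. That sits against the requirement for spastic cerebral palsy in section 3.1, and no control procedures or comparison are described, so they cannot be counted as one.

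Finally, a ratio to limb size assumes that muscle grows in proportion to the limb, which the documents do not establish for spastic muscle. It also adds noise: if a tape measurement has a random error of 1 to 2% per session (assumed), the change in CSA over segment length squared gains 2 × √2 × 1 to 2% = 2.8 to 5.7% per child. This is a good reason not to make a ratio the only primary outcome.

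**Conclusion.** The point holds in a bounded form. For muscle length and CSA at session 3, or at a session 2 held late in its window, the protocol lists nothing that would let growth be separated from a BTX-A effect. This follows from the text alone.

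Its size rests on outside assumptions: about 2 to 4% in length and 4 to 8% in CSA at 6 months, and roughly double that at 12 months, for children growing at the assumed rates. The effect on test results depends further on an unknown standard deviation.

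The documents do not support the broader claims that all comparisons are unscaled or that all visits and outcomes are affected. This is a gap that should be closed by a cheap addition to data collection; it does not invalidate the study. Limb size not recorded at a session cannot be recovered afterwards.

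**What to change.** 1. **Section 4.1:** add height and the length of the relevant limb segment (forearm, or upper arm if those muscles are treated) by tape at every session. Add the tape to section 4.3.
2. **Sections 4.4 and 7:** report muscle length and CSA adjusted for segment length, either as scaled values (length over segment length, CSA over segment length squared) or with segment length as a covariate, alongside the unscaled values.
3. **Sections 1 and 2.1:** word conclusions as change after BTX-A. Size adjustment reduces growth bias but does not turn an uncontrolled design into a controlled one.

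The cost is about 2 minutes per session, a short amendment, and some added measurement error in the scaled values, which is why the unscaled values are kept. Scanning the same muscle on an uninvolved side would give a within-child reference, but it is an extra procedure and is not needed for this fix.

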# 2. Study Objectives

## 2.1 Primary Objective:

The primary objective of this study is to investigate the effect of BTX-A on the anthropometric and mechanical characteristics of muscles and tendons at various time points after BTX-A injections in children with spastic upper extremity CP.

## 2.2 Secondary Objective:

The secondary objectives are to use of shear wave elastography in upper limb musculature to better understand if this tool can be used to estimate tendon stiffness and to use the results of this study and computational models to identify limits of suitability for muscles and tendons to aid in surgical treatment following BTX-A injections.

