## 6 Assessment and follow up

All ultrasound scans will be reported to and reviewed by the clinical care team so that in the event of incidental findings these can be appropriately investigated and acted upon.\_There will be no routine follow up for participants. The end of study is defined as the end of the third data collection session or the final data collection session for that participant.

The end of study is defined as the end of the third data collection session or the final data collection session for that participant.

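### The secondary objective in 2.2 is not matched by the data or by the outcome in 4.4: the elastography question has no reference measure and no outcome, and model-derived surgical limits could not be validated

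*Protocol*

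**What the plan says.** Protocol section 2.2 has two parts. The first is to use SWE in the upper limb "to better understand if this tool can be used to estimate tendon stiffness". The second is to use the study results with models to "identify limits of suitability for muscles and tendons to aid in surgical treatment following BTX-A injections". The introduction repeats the second aim and expects the work to support muscle and tendon selection and a more objective guideline.

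Section 4.4 gives one secondary outcome: "The secondary outcome measure is the comparison of computational models for data collected before and after BTX-A injections". The primary outcomes in the same section are tendon elasticity and muscle anthropometrics before and after injection.

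Section 4.1 says that every session consists of the procedures in 4.1.1 to 4.1.3: the SHUEE, SWE ultrasound, and the Modified Ashworth Scale with surface EMG. The tendon reading in 4.1.2 is "shear-wave velocity during the relaxed and stretched states of the origin and insertion tendons of the muscles to be injected with BTX-A", with a run of 10 images once the probe is aligned. Section 6 ends the study at the third or final data collection session.

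**The concern.** To learn whether a tool estimates a quantity, one needs either that quantity from another source or a situation in which its behaviour is known beforehand. A change in SWE from before to after BTX-A offers neither, because the true change in the tendon is unknown. If SWE moves, the tendon may have changed or the tool may be responding to something else. If it does not move, the tendon may be unchanged or the tool insensitive. The primary outcome relies on the tool whose usability section 2.2 treats as open.

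For the second part, a limit of suitability is a statement about where a muscle or tendon stops being useful in surgery. Without surgical results, a limit obtained from a model stays a property of that model. What is at stake is interpretation: the introduction points towards surgical selection in children, and an unvalidated limit could be read there as guidance.

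**Working it through.** The point is one of design and has no figure to reproduce. The check sets each aim against the data planned for it.

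| Aim in 2.2 | Data needed to test it | What the protocol collects | Outcome in 4.4 |
|---|---|---|---|
| Can SWE be used to estimate tendon stiffness? | SWE plus an independent stiffness measure (force or torque with elongation), or a contrast whose direction is known beforehand | Shear-wave velocity, relaxed and stretched; no independent stiffness measure | None |
| Limits of suitability for surgery after BTX-A | A criterion of suitability and, to validate it, surgical results | Inputs to models; no surgical result | Before-after comparison of models |

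**Could another procedure act as the reference?** The SHUEE (4.1.1, 4.2) scores spontaneous use, segment alignment, and grasp and release. The Modified Ashworth Scale (4.1.3) grades resistance to passive movement as an index of spasticity. Surface EMG records muscle activity. None measures tendon stiffness, and the equipment list in 4.3 contains no force, torque or elongation device.

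**Could an unseen analysis plan close the gap?** It could specify the models and a suitability criterion. It could not supply a stiffness reference or a surgical result, since no session records them.

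**What do the planned data allow?** The relaxed and stretched readings form a within-session contrast whose direction can be stated in advance: velocity is expected to rise with stretch (an assumption, to be written down beforehand). The 10 images allow repeatability to be examined within an acquisition, though not across probe repositioning. Together these inform feasibility and responsiveness, not agreement with true stiffness.

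**Would adding a reference measure be better?** Section 3.4 gives 8 participants. Take one pair of values per child and an assumed observed correlation r between SWE and a reference. The 95% interval is tanh(atanh(r) ± 1.96/√(n − 3)), and with n = 8 the half-width is 1.96/√5 = 0.877.

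- r = 0.9: atanh = 1.472; limits tanh(0.596) and tanh(2.349), that is 0.53 to 0.98.
- r = 0.7: atanh = 0.867; limits tanh(−0.009) and tanh(1.744), that is −0.01 to 0.94.

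Even a strong observed correlation would leave validity poorly determined at this size. That favours narrowing the aim over adding a measurement.

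**A related point on the conversion.** Section 4.1.2 states: "As the shear modulus is equal to the shear-wave velocity multiplied by the density of the tissue". The units do not agree. Density times velocity is (kg/m³)(m/s) = kg/(m²·s), whereas a modulus is a pressure, kg/(m·s²). Density times velocity squared has the right units. An outcome expressed in velocity itself does not depend on this conversion, but the sentence should be corrected.

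**The case against.** The strongest reply is that section 2.2 is exploratory. It aims to understand better whether the tool can be used and does not promise validation. The relaxed and stretched readings and the image sequence do give partial information. This stands. A reader might infer that neither part of the objective can be answered at all, and the documents do not support that. What remains is that 4.4 lists no outcome for the SWE question and that nothing collected can test the tool against stiffness.

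A second reply is that the limits are meant to come from models, so children need not be followed to surgery for a limit to be produced. This also stands. The absence of surgical results prevents validation, not production. The protocol does not describe the models, so one cannot say what they could or could not output.

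Two further inferences are tempting. One is that each child is observed through a single BTX-A course. Section 3.1 recruits children due to start treatment, and section 4.1 sets the third session at 6 months or later with no upper bound. Nothing limits a child to one course, and the number of courses is neither fixed nor recorded. The other is that the study fails to answer a question about continuous use. The introduction does say "it is important to know if the continuous use of BTX-A affects the performance of the associated tendon in future surgical intervention", but this is background: sections 2.1, 2.2 and 4.4 do not commit to it. Nor does "There will be no routine follow up for participants" in section 6 carry much weight, since it sits beside text on incidental findings and three sessions are still scheduled. The absence of surgical data rests on the session content in 4.1 and the end-of-study definition.

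**Conclusion.** The concern holds in a limited form: the secondary objective is not matched by the data or by the outcome in 4.4. The SWE part has no independent stiffness measure and no listed outcome, while the primary outcome presupposes the tool. The surgical part could yield model-derived limits, but the study has no means of validating them. Both parts of the secondary objective are affected. The before-after comparison of SWE readings and muscle anthropometrics can proceed as planned. The change should be made but is not critical.

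The conclusion assumes that 4.1.1 to 4.1.3 and 4.3 list everything measured, as section 4.1 says of the sessions. It makes no assumption about the number of BTX-A courses or about what the models output.

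**What to change.** Three changes of wording and one added outcome.

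1. **Section 2.2, first part.** Ask whether SWE is feasible and responsive in upper-limb tendons, in place of whether it can estimate stiffness.
2. **Section 4.4.** Add a secondary outcome from readings already planned in 4.1.2: for each tendon, the within-session difference in shear-wave velocity between stretched and relaxed states, with the expected direction stated beforehand; its repeatability across the 10 images; and the proportion of usable acquisitions, with usable defined in advance.
3. **Section 2.2, second part, and the matching introduction sentence.** Aim to describe the change in model outputs after the start of BTX-A. Label any suitability limits as exploratory and not validated against surgery. The sponsor should name the model outputs, which the protocol does not state.
4. **Section 4.1.2.** Correct the sentence relating shear modulus to velocity and density.

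The cost is a protocol amendment and a more modest stated claim. No new procedure, session or participant is needed. The added outcome supports statements about responsiveness only. A claim that SWE measures tendon stiffness would still need an independent reference, and 8 participants would give little precision for it.
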